20.0 Data Monitoring

20.1 Safety Review Committee

The Safety Review Committee (SRC) will review the safety and ethics of the trial by reviewing interim data after each cohort of treatment during recruitment to the Dose Escalation Cohort. The SRC will meet or communicate via teleconference at least after each dose level in the Dose Escalation Cohort has recruited at least 3 patients and they have received their first cycle of treatment, to review safety.

Safety reports will be periodically reviewed for the trial unless otherwise requested to determine patterns and trends of events, or to identify safety issues, which would not be apparent on an individual case basis. Detailed reports containing safety summaries will be prepared by the CTRU for the SRC every 3 months.

20.2 Trial Steering Committee (during the dose expansion phase only):

The Trial Steering Committee will review safety data and liaise with the SRC regarding safety issues, and periodically reviewing efficacy data in the dose expansion phase.

20.3 Data Monitoring

Data will be monitored for quality and completeness by the CTRU. Missing data will be chased until it is received, confirmed as not available or the trial is at analysis. The CTRU will reserve the right to intermittently conduct source data verification exercises on a sample of patients, which will be carried out by staff from the CTRU. Source data verification will involve direct access to participant medical records at the participating centres, and the central collection of copies of consent forms and other relevant investigation reports. A Trial Monitoring Plan will be developed and a Meeting Group Monitoring Schedule including primary endpoint and safety data will be defined and agreed by the Trial Management Group (TMG), if necessary.

20.4 Clinical Governance Issues

To ensure responsibility and accountability for the overall quality of care received by patients during the trial period, clinical governance issues pertaining to all aspects of routine management will be brought to the attention of the SRC, sponsor and, where applicable, to individual NHS Trusts.

21.0 Ethical and Regulatory Approvals

In conducting the trial, the Sponsor, LEEDS CTRU and sites shall comply with all laws and statutes, as amended from time to time, applicable to the performance of clinical trials including, but not limited to:

- the principles of ICH Harmonised Tripartite Guideline for Good Clinical Practice (CPMP/ICH/135/95) as set out in Schedule 1 (Conditions and Principles of Good Clinical Practice and for the Protection of Clinical Trial Subjects) of the Medicines for Human Use (Clinical Trials) Regulations 2004 and the GCP Directive 2005/28/EC, as set out in SI 2006/1928
- Human Rights Act 1998
- Data Protection Act 1998
- Freedom of Information Act 2000
- Human Tissue Act 2004
- Human Tissue Act (Scotland) 2006
- Medicines Act 1968
- Medicines for Human Use (Clinical Trials) UK Regulations SI 2004/1031, and subsequent amendments
- Good Manufacturing Practice
- the Research Governance Framework for Health and Social Care, issued by the UK Department of Health (Second Edition 2005) or the Scottish Health Department Research Governance Framework for Health and Community Care (Second Edition 2006)

21.1 Ethical Approval

The trial will be conducted in accordance with the World Medical Association Declaration of Helsinki entitled 'Ethical Principles for Medical Research Involving Human Subjects' (1996 version) and in accordance with the terms and conditions of the ethical approval given to the trial.

LEEDS CTRU will submit an application for favourable ethical opinion and will subsequently submit Annual Progress Reports to the REC, which will commence one year from the date of ethical approval for the trial.

21.2 Regulatory Approval

The trial will be conducted at approved trial sites in accordance with the trial protocol and the terms of the CTA granted by the MHRA.

21.3 Site Approvals

Local governance checks will be undertaken by local CLRNs associated with individual trial sites.

Evidence of approval from the Trust R&D for a trial site must be provided to LEEDS CTRU. Sites will only be activated when all necessary local approvals for the trial have been obtained.

21.4 Protocol Amendments

LEEDS CTRU will be responsible for gaining ethical and regulatory approvals, as appropriate, for amendments made to the protocol and other trial-related documents. Once approved, LEEDS CTRU will ensure that all amended documents are distributed to sites and CLRNs as appropriate.

Site staff will be responsible for acknowledging receipt of documents and for implementing all amendments.

21.5 Patient Confidentiality & Data Protection

Patient identifiable data, including date of birth, patient initials and NHS number will be required for the registration process and will be provided to LEEDS CTRU.

LEEDS CTRU will preserve patient confidentiality and will not disclose or reproduce any information by which patients could be identified. Data will be stored in a secure manner and LEEDS CTRU trials are registered in accordance with the Data Protection Act 1998 with the Data Protection Officer at UCL.

The CTRU will comply with all aspects of the 1998 Data Protection Act and operationally this will include:

- consent from participants to record personal details including name, date of birth, NHS ID, hospital ID
- appropriate storage, restricted access and disposal arrangements for participant personal and clinical details
- consent from participants for access to their medical records by responsible individuals from the research staff or from regulatory authorities, where it is relevant to trial participation
- consent from participants for the data collected for the trial to be used to evaluate safety and develop new research.
- participant name will be collected on the consent form when a participant is registered into the trial, but all other data collection forms that are transferred to or from the CTRU will be coded with a trial number and will include two participant identifiers, usually the participant's initials and date of birth.
- where central monitoring of source documents by CTRU (or copies of source documents) is required (such as scans or local blood results), the participant's name must be obliterated by site before sending
- where anonymisation of documentation is required, sites are responsible for ensuring only the instructed identifiers are present before sending to CTRU

If a participant withdraws consent from further trial treatment and / or further collection of data, their data and samples will remain on file and will be included in the final trial analysis.

The trial staff at the participating site will be responsible for ensuring that any data / documentation sent to the CTRU is appropriately anonymised as per instructions given by CTRU in accordance with the trial procedures to conform with the 1998 Data Protection Act.

22.2 Indemnity

University College London holds insurance against claims from patients for injury caused by their participation in the clinical trial. Patients may be able to claim compensation if they can prove that UCL has been negligent. However, as this clinical trial is being carried out in a hospital, the hospital continues to have a duty of care to the participant of the clinical trial. University College London does not accept liability for any breach in the hospital's duty of care, or any negligence on the part of hospital employees. This applies whether the hospital is an NHS Trust or otherwise.

Patients may also be able to claim compensation for injury caused by participation in this clinical trial without the need to prove negligence on the part of University College London or another party. Patients who sustain injury and wish to make a claim for compensation should do so in writing in the first instance to the Chief Investigator, who will pass the claim to the Sponsor's Insurers, via the Sponsor's office.

Hospitals selected to participate in this clinical trial shall provide clinical negligence insurance cover for harm caused by their employees and a copy of the relevant insurance policy or summary shall be provided to University College London, upon request.

23.0 Funding

Carfilzomib is provided free of charge for the trial duration by Amgen .

24.0 Publication Policy

All publications and presentations relating to the trial will be authorised by the Trial Management Group. The TMG will form the basis of the writing committee and advise on the nature of publications. Contributing site investigators in this trial will also be acknowledged. Data from all sites will be analysed together and published as soon as possible. Participating sites may not publish trial results prior to the first publication by the TMG or without prior written consent from the TMG. The trial data is owned by UCL. However, drug companies who have provided grants towards the trial will be permitted to see the draft manuscripts and make comments at least prior to submission for publication as detailed in the trial drug supply agreement. The ISRCTN number allocated to this trial will be quoted in any publications resulting from this trial.

The trial will be registered with an authorised registry, according to ICMJE Guidelines, prior to the start of recruitment.

The success of the trial depends upon the collaboration of all patients. For this reason, credit for the main results will be given to all those who have collaborated in the trial, through authorship and contributor ship. Uniform requirements for authorship for manuscripts submitted to medical journals will guide authorship decisions. These state that authorship credit should be based only on substantial contribution to:

- conception and design, or acquisition of data, or analysis and interpretation of data
- drafting the article or revising it critically for important intellectual content
- and final approval of the version to be published
- and that all these conditions must be met (www.icmje.org).

In light of this the Chief Investigator and relevant senior CTRU staff will be named as authors in any publication. Dependent on the number of participating centres and journal restrictions, wherever possible all Principal Investigators and at least two CTRU staff will be named as authors.

Publication of emerging safety data in the form of abstracts for oral or poster presentation, or journal letters is permitted. However no formal manuscript publication is permitted until the final analysis of the trial data has been completed. All abstracts and letters must be reviewed by at least the Chief Investigator and CTRU trial statistician. The release of any data prior to the end of the trial must be approved by the Safety Review Committee. Amgen will review any resulting publications prior to submission as detailed in the contract.

APPENDIX 1: ABBREVIATIONS

ABPI	Association of British Pharmaceutical Industry
ADL	Activities of Daily Living
AE	Adverse Event
AL	Refers to the serum free light chain fibrils that are produced in this type of Amyloidosis
ALP	Alkaline phosphatase
ALT	Alanine transaminase
AML	Acute Myeloid Leukaemia
ANC	Absolute Neutrophil Count
APTT	Activate partial thromboplastin time
AR	Adverse Reaction
ASCT	Autologous stem cell transplantation
AST	Aspartate aminotransferase
AUC	Area Under the Curve
Bcl	B-cell lymphoma
BUN	Blood urea nitrogen
CAM	Cell Adhesion Molecule
CD	Cluster of differentiation
CEA	Carcinoembryonic Antigen
CI	Chief Investigator
CLRN	Comprehensive local research network
CR	Complete response
CrCl	Creatinine clearance
CRd	A chemotherapy regimen of Carfilzomib, lenalidomide, and Dexamethasone
CRF	Case Report Form
CR UK	Cancer Research UK
CT	Computerised Tomography
CTA	Clinical Trial Authorisation
CTAAC	Clinical Trials Advisory & Awards Committee
CTCAE	see NCI CTCAE
CTD	Chemotherapy regimen containing cyclophosphamide, Thalidomide & Dexamethasone
CTDa	Attenuated CTD
CTRU	Clinical Trials Research Unit
CTSA	Clinical Trial Site Agreement
CVD	Chemotherapy regimen containing Bortezomib, Cyclophosphamide & Dexamethasone
CXR	Chest X-Ray
DFS	Disease Free Survival
DH	Department of Health
DI	Dose intensity
DLT	Dose Limiting Toxicity
DOR	Duration of Response
DPA	Data Protection Act
DSUR	Development Safety Update Report
ECG	Electrocardiogram
ECOG	Eastern Cooperative Oncology Group
EDTA	Ethylene Diamine Tetra Acetate
eGFR	Estimated glomerular filtration rate
EudraCT	European Clinical Trials Database
FBC	Full Blood Count
FLC	Free Light Chain
G-CSF	Granulocyte Colony Stimulating Factor
GFR	Glomerular Filtration Rate
GI	Gastro-intestinal
GGT	Gamma glutamyl-transpeptidase/transferase
Hb	Haemoglobin
HIV	Human Immunodeficiency Virus
HL	Hodgkin's lymphoma

HUS	Haemolytic uraemic syndrome
IκBα	Inhibitor protein: I kappa B alpha-associated protein kinase
IB	Investigator's Brochure
ICH GCP	International Conference of Harmonisation-Good Clinical Practice
IDMC	Independent Data Monitoring Committee
IDMD	Intermediate dose melphalan and Dexamethasone
IL	Interleukin
ImiD	Immunomodulatory Drug
IMP	Investigational Medicinal Product
IMWG	International Myeloma Working Group
INR	International Normalised Ratio
ISRCTN	International Standard Randomised Controlled Trial Number
IUD	Intrauterine Device
IUS	Intrauterine System
IV	Intravenous
KTD	Chemotherapy regimen containing Carfilzomib, Thalidomide & Dexamethasone
LDH	Lactate Dehydrogenase
LFT	Liver Function Tests
LLN	Lower Limit of Normal
LVEF	Left ventricular ejection fraction
MDS	Myelodysplastic Syndrome
MM	Multiple Myeloma
MP	Melphalan & Prednisolone
MR	Maximum response
MRC	Medical Research Council
MTD	Maximum Tolerated Dose
REC	Research Ethics Committee
MRI	Magnetic Resonance Image
MHRA	Medicines and Healthcare products Regulatory Agency
NAC	See UK NAC
NCI	National Cancer Institute
NCI CTCAE	National Cancer Institute Common Terminology Criteria for Adverse Events
nCR	Near Complete Response
NCRI	National Cancer Research Institute
NCRN	National Cancer Research Network
NHL	Non-Hodgkin's lymphoma
NICE	National Institute of Clinical Excellence
NIHR	National Institute for Health Research
NF-κB	Nuclear Factor- κ B
NR	Not meeting Free Light Chain criteria for Complete Response (CR) or Partial Response (PR)
NRES	National Research Ethics Service
NT-proBNP	N-terminal prohormone of brain natriuretic peptide
NYHA	New York Heart Association
ORR	Overall response rates
OS	Overall Survival
PA	Posteroanterior
PAD	Chemotherapy regimen containing Bortezomib, Doxorubicin & Dexamethasone
PD	Progressive Disease
PFS	Progression Free Survival
PI	Principal Investigator
PO	By mouth
PR	Partial Response
PRES	Posterior reversible encephalopathy syndrome
PT	Prothrombin time
RD	Recommended Dose
RDI	Relative dose intensity
REC	Research Ethics Committee
RECIST	Response Evaluation Criteria in Solid Tumours
RHC	Regional Haematology Centre (Site)

RPLS	Reversible posterior leukoencephalopathy syndrome
R/RMM	Relapsed/refractory multiple myeloma
SAE	Serious Adverse Event
SAR	Serious Adverse Reaction
SAP	Serum Amyloid Protein
SC	Subcutaneous
SCC	Stem cell collection
SD	Stable Disease
SOP	Standard operating procedure
SPC	Summary of Product Characteristics
SRC	Safety Review Committee
SSA	Site Specific Assessment
SUSAR	Suspected Unexpected Serious Adverse Reaction
TLS	Tumour lysis syndrome
TMF	Trial Master File
TMG	Trial Management Group
TRM	Treatment Related Mortality
TSC	Trial Steering Committee
TTP	Time to progression
UCL	University College London
U&E	Urea and Electrolyte
UK NAC	UK National Amyloidosis Centre (Royal Free Hospital)
ULN	Upper Limit of Normal
VAD	Chemotherapy regimen containing vincristine, doxorubicin and Dexamethasone
VGPR	Very Good Partial Response
WBC	White Blood Cells

APPENDIX 2: DEFINITION OF AMYLOIDOSIS, MYELOMA AND RELATED DISEASES

Amyloid

- Tissue biopsy showing red-green birefringence in cross polarised light when stained with Congo red by Puchtler's method

Overt Non-Amyloid manifestations of Multiple Myeloma

- Lytic bony lesions (>4 if limited to skull only)
- Hypercalcaemia, hyperviscosity or plasmacytomata

Amyloid-related organ involvement causing organ dysfunction

For details please refer to Gertz et al. Definition of organ involvement and treatment response in immunoglobulin light chain amyloidosis (AL): a consensus opinion from the 10th International Symposium on Amyloid and Amyloidosis. Am J Hematol. 2005 Aug;79(4):319-28.

Defining organ involvement	
Kidney	24-hour urine protein >0.5 g per day, predominantly albumin
Heart	Echo: mean left ventricular wall thickness >12 mm, no other cardiac cause or severe diastolic dysfunction in presence of NT-ProBNP >150 pMol/L and low voltage complexes on ECG without any other cause for these abnormalities
Liver	Total liver span >15 cm in the absence of heart failure or alkaline phosphatase >1.5 times institutional upper limit of normal
Gastrointestinal tract	Symptomatic GI disturbance with or without direct biopsy verification with
Nerve	Peripheral: clinical; symmetric lower extremity sensorimotor peripheral neuropathy Autonomic: gastric-emptying disorder, pseudo-obstruction, voiding dysfunction not related to direct organ infiltration, postural hypotension
Soft tissue	Tongue enlargement, clinical Arthropathy Myopathy by biopsy or pseudohypertrophy Lymph node enlargement

Number of organs involved by amyloid

One to 5 of the following organ systems could be involved by amyloid;

- Renal
- Gastro-intestinal (including liver)
- Cardiac
- Nerves (peripheral and/or autonomic)
- Miscellaneous (e.g. significant soft tissue, factor X deficiency, adrenal insufficiency)

APPENDIX 3: ECOG GRADES OF PERFORMANCE STATUS AND NYHA CLASS

Grade	Summary	Description
0	Normal	Able to carry out all normal activity without restriction
1	With effort	Restricted in physically strenuous activity; ambulatory, can do light work
2	Restricted	Ambulatory and capable of all self-care but unable to carry out any work; up and about more than 50% of waking hours
3	Dependent	Capable of only limited self-care; confined to bed or chair for more than 50% of waking hours
4	Immobile	Completely disabled; cannot carry out any self-care; totally confined to bed or chair

NYHA CLASS

Class I	Patients with no limitation of activities; they suffer no symptoms from ordinary activities.
Class II	Patients with slight, mild limitation of activity; they are comfortable with rest or with mild exertion.
Class III	Patients with marked limitation of activity; they are comfortable only at rest.
Class IV	Patients who should be at complete rest, confined to bed or chair; any physical activity brings on discomfort and symptoms occur at rest.

APPENDIX 4: DEFINITIONS OF RESPONSE

(based on IMWG criteria 2006 and amyloidosis consensus criteria 2005)

Haematological Response:

CR	Negative immunofixation of serum and urine (serum alone in anuric patients) AND Normal FLC concentration and kappa/lambda FLC ratio (FLC ratio alone in renal failure) AND ≤5% plasma cells in bone marrow ^a without clonality by immunohistochemistry or immunofluorescence ^a
VGPR ^b	>90% reduction in serum paraprotein or abnormal component of FLC or dFLC over the starting value or dFLC <40mg/L
PR	≥50% decrease in aberrant FLC concentration or dFLC (or ≥50% decrease in dFLC if renal failure) or serum paraprotein but not fulfilling criteria for CR or VGPR
MR	>25% but <50% decrease in aberrant FLC or dFLC or paraprotein
NR	Not meeting FLC criteria for CR, PR or MR

Abbreviations: CR, complete response; FLC, free light chain; PR, partial response; NR, no response.

Plateau	2 consecutive FLC samples or serum paraprotein (at least 2 weeks apart) showing the aberrant (monoclonal) light chain concentration to be abnormal but stable (within 20% of each other). In the context of progressive renal impairment, the κ/λ ratio or dFLC rather than absolute FLC concentration should remain stable (i.e. within 20%).
---------	---

^a Confirmation with repeat bone marrow biopsy only if done, not mandatory. Presence/absence of clonal cells is based upon the κ/λ ratio. An abnormal κ/λ ratio by immunohistochemistry and/or immunofluorescence requires a minimum of 100 plasma cells for analysis. An abnormal ratio reflecting presence of an abnormal clone is κ/λ of >4:1 or <1:2. Alternatively, the absence of clonal plasma cells can be defined based on the investigation of phenotypically aberrant PC. The sensitivity level is 10^{-3} (less than one phenotypically aberrant PC within a total of 1000 PC). Examples of aberrant phenotypes include (1) CD38^{dim} and CD56^{strong} and CD19⁻ and CD45⁻; (2) CD38^{dim} and CD138⁺ and CD56⁺⁺ and CD28⁺; (3) CD138⁺, CD19⁻ CD56⁺⁺, CD117⁺.

APPENDIX 4 CONTINUED OVERLEAF.....

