6.3.1 Inclusion Criteria

Patients with the following characteristics are eligible for this study:

1. Aged 18 years or greater
2. Diagnosis of systemic AL amyloidosis with
 - i. exclusion of genetic mutations associated with hereditary amyloidosis and immunohistochemical exclusion of AA and TTR amyloidosis as appropriate
 - ii. Amyloid-related organ dysfunction or organ syndrome (see Appendix 2)
3. Measurable clonal disease
4. Clonal relapse after previous chemotherapy or autograft stem cell transplant OR refractory clonal disease to previous chemotherapy or stem cell transplant
5. Capable of providing written, informed consent and willing to follow study protocol
6. Life expectancy \geq 6 months
7. ECOG performance status of 0-2
8. Platelet count \geq $50 \times 10^9/l$
9. Neutrophil count \geq $1 \times 10^9/l$
10. Haemoglobin \geq 8g/dL
11. Bilirubin < 2 times or Alkaline phosphatase < 4 times upper limit of normal.
12. Female participants of child-bearing potential must have a negative pregnancy test prior to treatment and agree to use dual methods of contraception for the duration of the study and for 30 days following completion of study. Male participants must also agree to use a barrier method of contraception for the

duration of the study and for 90 days following completion of study if sexually active with a female of child-bearing potential. Women who could become pregnant must have taken precautions not to become pregnant for 1 month before the start of the study. Because of the increased risk of venous thromboembolism in patients, combined oral contraceptive pills are not recommended.

13. Participants must be willing to comply with the Celgene pregnancy prevention programme for Thalidomide

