19.0 Statistical considerations

19.1 Sample size

In the dose escalation phase of this study, a minimum of 6 (3 at dose level 0 and 3 at dose level -1) and a maximum of 18 (6 at dose level 0 1 and 2) patients will be recruited in a 3+3 design with cohorts of between 3 and 6 patients, in order to determine maximum tolerated dose and recommended dose.

At the recommended dose level identified, a further 20 patients will be recruited to further assess safety and toxicities at the RD.

The secondary objective of assessing activity will be primarily assessed by the clonal response rate.

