APPENDIX 4 CONTINUED FROM PREVIOUS PAGE

Haematological Relapse:

From CR	Increase in the aberrant serum free light chain concentration to outside the normal range and by a factor of ≥ 2 from that at the time of CR or re-appearance of the original paraprotein
From PR or VGPR:	Increase in the aberrant free light chain concentration by a factor of ≥ 2 from that at the time of PR ($\geq 50\%$ change in ratio away from normal in patients with renal failure) or doubling of the serum paraprotein level (if starting $>5\text{g/L}$) or doubling and increase of serum paraprotein to $>5\text{g/L}$ (if starting $<5\text{g/L}$)

Organ Response:

Heart	Interventricular septal thickness decreased by 2 mm or 10% improvement in ejection fraction or a 30% and 35 pMol/L reduction in NT-ProBNP (only applicable if there is no change or $<25\%$ improvement in renal function) or significant improvement in lateral wall TDI S wave and E/E' ratio
Kidney	50% decrease (at least 0.5 g/day) in 24-hr urinary protein loss (urine protein must be >0.5 g/day pretreatment) without fall in creatinine clearance of $\geq 25\%$ from baseline
Liver	50% decrease in abnormal alkaline phosphatase value or a decrease in liver size radiographically by at least 2 cm
Nerve	Improvement in electromyogram nerve conduction velocity (rare)
Soft tissue	Definite clinical and/or radiographic improvement with associated functional improvement in affected tissue

Organ Progression:

Heart	Interventricular septal thickness increased by >2 mm compared with baseline or 20% decline in ejection fraction
Kidney	50% increase (at least 1 g/day) in 24-hr urinary protein loss to >1 g/day OR Sustained fall in creatinine clearance of $\geq 25\%$ from baseline
Liver	50% increase of alkaline phosphatase from the lowest value
Nerve	Progressive neuropathy by electromyography or nerve conduction velocity
Soft tissue	Definite clinical and/or radiographic deterioration with associated functional deterioration in affected tissue

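### As the response table reads, dFLC below 40 mg/L alone is enough for VGPR, so a treated patient already below 40 mg/L at baseline can count as a clonal responder with no fall in the clone

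*Protocol*

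**What the plan says.** Protocol Appendix 4 defines VGPR as ">90% reduction in serum paraprotein or abnormal component of FLC or dFLC over the starting value or dFLC <40mg/L". The part that matters here is the end of that row, "over the starting value or dFLC <40mg/L". The PR row needs a fall of at least 50% and applies to patients "but not fulfilling criteria for CR or VGPR", so VGPR ranks above PR. The MR row needs ">25% but <50% decrease in aberrant FLC or dFLC or paraprotein".

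Protocol 18.3 and SAP 2.3.2 define clonal response as PR or better, so every VGPR counts. Neither section sets a condition on baseline dFLC.

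On entry, Protocol 6.3.1 requires "Measurable clonal disease" without a number, together with clonal relapse or refractory clonal disease. The relapse rows of Appendix 4 allow relapse from CR to be declared on "re-appearance of the original paraprotein", or on an aberrant light chain that is outside normal and at least doubled. The per protocol set (Protocol 19.2, SAP 3.3) requires one carfilzomib dose, one post-baseline efficacy assessment and no deviation relevant to efficacy.

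Protocol 19.1 gives the endpoint its weight: "The secondary objective of assessing activity will be primarily assessed by the clonal response rate".

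**The concern.** The other routes to PR or VGPR in Appendix 4, apart from CR, measure change from a starting value. The dFLC route to VGPR measures a level. A level is a sound criterion only for a patient who started above it. For a patient who enters below 40 mg/L, a stable value, or a rise that stays below 40 mg/L, meets the rule at the first post-baseline sample.

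Such patients can enter on the wording as it stands. A patient whose relapse shows mainly in paraprotein, or as a doubling from a low light chain level, need not have dFLC of 40 mg/L or more.

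At stake is the clonal response rate, which is meant to give an understanding of activity for the design of later trials. Maximum response and time to maximum response use the same categories and would inherit the problem.

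**Working it through.** The documents state no target response rate, power or error rate for clonal response, so there is no planned figure to reproduce. The check has three parts.

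**1. Fall needed to reach dFLC below 40 mg/L from baseline B.** The formula is max(0, 1 − 40/B).

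| Baseline dFLC (mg/L) | Fall needed |
|---|---|
| below 40 | 0% |
| 45 | 11.1% |
| 50 | 20.0% |
| 53.3 | 25.0% |
| 60 | 33.3% |
| 80 | 50.0% |
| 400 | 90.0% |

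Below 40 mg/L no fall is needed. From 40 to about 53 mg/L, VGPR can be reached with less than the fall required for MR. From 40 to 80 mg/L it can be reached with less than the fall required for PR. For example, 45 to 39 mg/L is (45 − 39)/45 = 13%.

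**2. Weight of one patient.** Protocol 8.1.3 requires at least 6 patients at the recommended dose before expansion, and Protocol 19.1 adds 20. That gives 6 + 20 = 26, and 1/26 = 3.8 percentage points. This is the most one patient can add, and applies only if that patient would otherwise be a non-responder.

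**3. Effect on the reported rate.** Let f be the share of patients who start below 40 mg/L and stay there. Let p be the true rate of PR or better, taken as equal in patients above and below 40 mg/L. The documents give neither, so both are assumptions.

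- Reported rate = f + (1 − f)p
- Net inflation = f + (1 − f)p − p = f(1 − p)

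| f | Reported rate, p = 0 | p = 20% | p = 40% | p = 60% | Inflation at p = 40% |
|---|---|---|---|---|---|
| 5% | 5% | 24% | 43% | 62% | 3 points |
| 10% | 10% | 28% | 46% | 64% | 6 points |
| 20% | 20% | 36% | 52% | 68% | 12 points |

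The p = 0 column is the ceiling: inflation then equals f, or 5 to 20 points.

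The chance of at least one such patient among 26 is 1 − (1 − f)^26, which is 74%, 94% and 99.7% at f = 5%, 10% and 20%. Even the smallest assumed share makes it more likely than not that the case arises.

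**The case against.** The strongest objection is the footnote. The VGPR row carries a marker b, and only note a appears in the copy I could read. A baseline condition on VGPR could well sit in that note. This stands: the point is about the wording as available, and the sponsor can settle it by looking.

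Second, a reader might infer that an untreated patient can count as a responder. The documents do not support that. Efficacy analyses use the per protocol set, which needs at least one carfilzomib dose and a post-baseline assessment. The supportable statement is that a treated patient can be counted with no fall.

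Third, the entry argument is partly inference. Protocol 6.3.1 does not cite the relapse rows of Appendix 4, and measurable disease must be met as well as relapse or refractoriness. Sites may apply a light chain minimum in practice. None is written, however, and a patient with measurable paraprotein and low dFLC meets the criteria as worded. How many such patients there will be is unknown.

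Fourth, a reader might take the whole share f as the bias. That assumes none of these patients would truly respond. The net effect is f(1 − p), which is smaller for any p above zero.

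Fifth, the stakes are bounded. The endpoint is secondary and descriptive, SAP 5.2 rules out formal testing, and responses at 3 and 6 months are tabulated by category. The tables would show how many patients reached VGPR but not by which route, so the reader could not undo the effect.

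Finally, the NR row, "Not meeting FLC criteria for CR, PR or MR", omits VGPR and ignores paraprotein. A patient with a 60% paraprotein fall and flat light chains then fits both PR and NR. A reader might count this as a further source of inflation, but it is not: applied literally, NR would lower the rate.

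**Conclusion.** The point holds, subject to the text of footnote b. The rule as written can score a treated patient with no fall in the clone as a responder on the main activity measure, and nothing in the entry criteria, the analysis set or SAP 2.3.2 prevents it. This is a fault in a stated rule rather than a missing detail.

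The size depends on an unknown share. For f of 5% to 20%, inflation is about 3 to 12 points at p = 40%, with a ceiling of 5 to 20 points at p = 0.

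Patients who start between 40 and 80 mg/L can also reach VGPR with less than a 50% fall, and a reader might infer that such a fall should be required. The documents do not compel that. Appendix 4 states that it is based on published criteria, and an added 50% requirement would be a new hybrid: a patient going from 60 to 35 mg/L (42%) would move from VGPR to MR. The defect that clearly needs repair is the zero-fall case.

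**What to change.** First check footnote b. If it already sets a baseline condition, repeat that condition in SAP 2.3.2. If it does not, change Appendix 4 and SAP 2.3.2 for the endpoint analysis only:

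- Allow the dFLC below 40 mg/L route to VGPR only when baseline dFLC was at or above 40 mg/L.
- Assess patients who start below 40 mg/L by paraprotein where it is measurable. Otherwise list them as not evaluable by dFLC.
- Report the clonal response rate with and without these patients.
- As a minor wording point, let NR read: not meeting criteria for CR, VGPR, PR or MR.

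Under the assumptions above, with p = 40%, the expected rate among evaluable patients returns from 43%, 46% or 52% (f = 5%, 10%, 20%) to 40%.

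The cost is wording only, because Protocol Appendix 6 already has serum free light chains measured at baseline. The downside is a possibly slightly lower reported rate and a few patients not evaluable by dFLC.

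Protocol 9.4 and 11.2 also tie continuation after cycle 3 to response. The sponsor should reconcile those sections with any change to the table; no clinical rule is proposed here.
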